1.0 Protocol Summary

| Study Dumoso | • Patient Cohort |
|--|---|
| Study Purpose | Patient Conort The purpose of the research is to implement and evaluate a nurse-led clinical program designed to improve screening, referral, and treatment for sexual dysfunction in gynecological cancer patients. Nurse Cohort The purpose of the research is to increase knowledge and confidence in sexual dysfunction screening, referral and treatment among gynecologic cancer nurses. |
| Research Procedures | The primary research procedures are: |
| | Patient Cohort Assess effectiveness of the nurse led clinical sexual dysfunction program via number of referrals and treatments in the chart before and after the intervention in gynecologic cancer patients. Assess improvement in sexual dysfunction in gynecologic cancer survivors via the Female Sexual Function Index (FSFI). Nurse Cohort Increase gynecologic nurses' knowledge and confidence of sexual dysfunction screening, referral and treatment using the Knowledge, Attitude, and Practice Survey in Healthcare (KAP), and the Evidence Based Nursing Practice Self-Efficacy Scale (EPSE). |
| Subject Population | Patient Cohort The study will enroll gynecological cancer patients who have completed treatment within the past twelve months. Nurse Cohort The study will enroll gynecologic oncology nurses in an outpatient comprehensive cancer center |
| Duration of Subject's Participation | Patient Cohort The study involves participation of patient subjects at multiple time points. The total patient study participation is 12 weeks. Nurse Cohort The study includes the participation of nurse subjects at two time points: pre and post education of sexual dysfunction screening and treatment. |

| • The total study duration is 2 hours. Nurses will have 4 |
|---|
| weeks to complete the 2 hours. |

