2.0 Background, Rationale

- Sexual dysfunction (SD) is a common issue among female cancer survivors, profoundly affecting their quality of life (Sousa Rodrigues-Guedes et al., 2022). Sexual dysfunction is highly prevalent among gynecological oncology patients, with rates reaching up to 90% (Kaufman et al., 2024).
- Discussion about sexual dysfunction between patients and healthcare providers are often limited, with reports indicating that such conversations occur in as few as 27.9% of cases (Sousa Rodrigues-Guedes et al., 2022). Several barriers contribute to this communication gap, including healthcare providers feeling unqualified or unprepared, facing time constraints, lacking referral resources, possessing limited knowledge, and being unsure how to broach the topic (Chou et al., 2023; Kaufman et al., 2024; Trachtenberg et al., 2019).
- Unaddressed sexual dysfunction can contribute to psychological distress, which in turn
 is associated with higher cancer incidence, increased cancer-specific mortality, and
 worsened survival outcomes (Wang et al., 2020).
- Sexual dysfunction negatively impacts mental, emotional, and relational well-being, contributing to lower HRQOL, an important predictor of morbidity and all-cause mortality in cancer survivors (DuMontier et al., 2018; Sitlinger & Zafar, 2019).
- Depression and anxiety linked to untreated sexual dysfunction can lead to higher emergency department use, longer hospital stays, and healthcare costs that are nearly double those of patients without these conditions (Birch et al., 2023; Masbach et al., 2020).
- Many interventions for sexual health have been investigated. These include
 psychoeducational and psychotherapeutic interventions, exercise programs, hormone
 replacement therapy administration, pelvic floor physical therapy, and health provider
 and patient education (Sopfe et al., 2021).
- There has been success in nurse-led rehabilitation programs that focus on a multimodal approach to sexual dysfunction in gynecological cancer survivors (Chow et al., 2023; Seaborne et al., 2021; Hungr et al., 2020).

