4.3.1 Consent Description

Patient Cohort

APP/Co-PI, [name], will identify patients via medical records. Potential participants will be contacted directly by APP/Co-PI through an IRB-approved email message based on the HRP-661 Direct to Patient Recruitment Letter. The patient will be given the opportunity to decline to be contacted, as indicated in the email. The APP/Co-PI will give the patient a reasonable amount of time to agree to or decline to be contacted after the email is sent. If the patient has already been approached by a treating physician about participation in this study, or if the patient has been sent the recruitment letter and has not declined to be contacted, the APP/Co-PI will reach out to the by phone. In the first conversation with the potential participant, the APP/Co-PI will explain the study carefully by going through the consent form via telephone script. The patient will be given the option to decline or defer participation, or, if interested, to sign the ICF by electronic signature via Docusign. The APP/Co-PI will send the potential participant the DocuSign link to the electronic consent form. Those who prefer to complete the consent form in person will have the option to do so electronically on a tablet or on paper. Patients will be highly encouraged to follow up with the study team before signing should they have any additional questions. If the patient indicates they plan to sign the consent form, the APP/Co-PI will follow up with another phone call if necessary to answer any remaining questions. All patients who participate will receive a surveillance visit with an additional focus on sexual health component with the Advanced Practice Provider ([name]). However, only patients who complete the pre-and post-FSFI survey and complete the APP visit will be involved in the study. The FSFI survey will be submitted to the patient and completed via REDcap.

Nurse Cohort

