5.0 Study Design and Procedures

5.1 Schedule of Events:

| Procedures | Screening Period | Visit #1 | Telephone Call | 8-10 weeks after Visit #1 |
|--|------------------|----------|----------------|------------------------------|
| Informed Consent | R | | | |
| FSFI Survey | R | | | |
| Medical History | | S | | |
| Medication History | | S | R | |
| Pelvic Exam | | S | | |
| Focused Sexual Health Questions | | S | | |
| Sexual Health Plan of Care, Education, and Referrals | | S | | |
| FSFI Survey | | | | R |

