5.3 Description of Study Procedures

Patient Cohort

The study involves the participation of patients at multiple time points. The study procedures will assess the patients sexual function using the FSFI prior to the APP sexual health visit and post APP sexual health visit and telephone follow up call. Patients will be recruited through clinical chart identification.

This study involves the participation of registered nurses at multiple time points. The study procedures will assess the nurses' knowledge and confidence using the KAP and EPSE survey before sexual health program and again post education at the end of the study. The survey results will remain anonymous for both the pre and post-test. Nurse subjects will be recruited via email, and staff weekly huddles to complete both surveys.

Medical Record/Clinical Record Review:

Patient Cohort

This study involves review of medical records of patients included in this study. The questionnaire will be administered once at baseline (prior to the APP visit) and at the end of the study (after the telephone follow up call performed 8-10 weeks post APP visit). The study will collect sensitive information. This information is routinely collected per standard of care as as part of clinical care on a regular basis. A study code will be included on the questionnaire. The questionnaire will not be linked to each other and will be administered at two different time points.

- Female Sexual Function Index (FSFI)
 - o The FSFI is a validated tool that addresses five domains: desire, subjective arousal, lubrication, orgasm, satisfaction, and pain/discomfort. It encompasses nineteen self-measurement items that provides a score on overall levels of sexual function (Meston et al., 2020).
- Chart review to count the number of referrals and treatments for sexual dysfunction before and after the nurse led sexual health clinical program intervention

Nurse Cohort- N/A

Education:

Nurse Cohort

- The educational content will come from the After Cancer Solutions for Sexual Health Program, a non-profit developed with input from a cancer survivor and specialists to provide evidence-based education for providers and patients (After Cancer, 2025). The program, including the "About Us" pilot and "30 Second Message Workshop," is active across Iowa and aims to normalize sexual health discussions, build provider confidence, and guide appropriate referrals (After Cancer, 2025).
 - o 30 second message workshop

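### The before/after chart count of referrals and treatments can rise with no change in care, because sexual-health questioning is added only from Visit #1 and no treatment start date is collected

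*Protocol*

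**What the plan says.** Section 1.0 (Research Procedures, Patient Cohort) lists as its first item: "Assess effectiveness of the nurse led clinical sexual dysfunction program via number of referrals and treatments in the chart before and after the intervention". Section 5.3 gives the method: "Chart review to count the number of referrals and treatments for sexual dysfunction before and after the nurse led sexual health clinical program intervention". There is no control group, so this measure rests entirely on the difference between the two periods.

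Several parts of the Protocol bear on how complete the chart is in each period:

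- Section 1.0 describes the program as "designed to improve screening, referral, and treatment for sexual dysfunction in gynecological cancer patients", so more screening is one of its aims.
- Section 4.3.1 says that participating patients "will receive a surveillance visit with an additional focus on sexual health component".
- In the Section 5.1 schedule, the screening period holds only consent and the FSFI. "Focused Sexual Health Questions" appears at Visit #1 only. "Medication History" appears at Visit #1 and again at the telephone call.
- Section 2.0 describes discussion of sexual dysfunction as limited, "with reports indicating that such conversations occur in as few as 27.9% of cases".
- Section 6.3 lists dates of surgery, chemotherapy and radiation, earlier reports of sexual dysfunction, and referrals to and visits with named services. It lists no treatment for sexual dysfunction and no start date for one.

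**The concern.** The two counts come from the same chart, but the chart is not filled in the same way in the two periods. Before Visit #1, a treatment the clinic did not order (something bought without prescription, or care from an outside therapist) reaches the chart only if somebody raised the subject. From Visit #1 onward the program raises it systematically. A patient whose care has not changed can therefore contribute nothing before and one item after.

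If that happens often enough, improved documentation is reported as improved care on a measure that Section 1.0 ties to effectiveness. Equal observation windows or per-month rates would not remove the problem, because the difference lies in what gets recorded and not in how long patients are observed. Nor can it simply be left to a later analysis. If no start date is collected, there is nothing with which to separate a new treatment from a newly charted one.

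**Working it through.** The Protocol gives no expected count, target or test for this measure, so there is no stated figure to reproduce. The check has two parts.

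**1. Ascertainment by period, from the text**

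| | Before Visit #1 | Visit #1 and after |
|---|---|---|
| Scheduled elicitation (5.1) | None beyond consent and the FSFI | Focused questions and medical and medication history at Visit #1; medication history at the call |
| Background rate of discussion (2.0) | As low as 27.9% | Raised by design (1.0, 4.3.1) |
| Date by which to classify a treatment (6.3) | None listed | None listed |

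In-house orders enter the chart when they are made, in either period. The asymmetry therefore concerns items not ordered in-house.

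**2. Illustration of size**

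Input from the Protocol: 35 patients recruited and 80% completing (Section 8.1), so N = 35 × 0.80 = 28. Section 4.3.1 limits the study to completers.

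Assumptions, none of them given in the documents:

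- u, the share of patients with one outside item in use, is the same before and after (no change in care), and is varied from 10% to 50%.
- d, the probability that such an item was charted before Visit #1, is 27.9%, 50% or 80%. The first value borrows the Section 2.0 discussion rate as a stand-in for a charting rate.
- Charting from Visit #1 onward is complete, and items charted earlier are still counted afterwards.

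Formulas: count before = N × u × d; count after = N × u; ratio = 1/d.

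| u | After | Before, d = 27.9% | Before, d = 50% | Before, d = 80% |
|---|---|---|---|---|
| 10% | 2.8 | 0.78 | 1.4 | 2.24 |
| 30% | 8.4 | 2.34 | 4.2 | 6.72 |
| 50% | 14.0 | 3.91 | 7.0 | 11.2 |
| Ratio | | 1/0.279 = 3.58 | 1/0.5 = 2.0 | 1/0.8 = 1.25 |

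The ratio does not depend on u or N. At d = 100% it is 1.0 and there is no bias. If charting from Visit #1 reaches only 90%, the ratios become 0.9/0.279 = 3.23, 0.9/0.5 = 1.8 and 0.9/0.8 = 1.125.

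**Dilution in the total count.** In-house items are captured alike in both periods, so they pull the overall ratio toward 1. Suppose, as a further assumption, that they are as numerous as the outside items and unchanged. The overall ratio is then (1 + 1)/(1 + d): 2/1.279 = 1.56, 2/1.5 = 1.33 and 2/1.8 = 1.11 for the three values of d.

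**The case against.** The strongest reply is that the Protocol never says items are sorted by the date they were first charted. A treatment found at Visit #1 to be already in use is naturally a before item, and Section 6.3 does collect earlier reports of sexual dysfunction and referrals. This stands in part. The attribution rule is unstated, so the artefact is conditional on how the abstractor proceeds. But Section 1.0 words the measure as what is in the chart before and after, and Section 6.3 provides no date by which treatments could be sorted otherwise.

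A reader might infer that the bias always favours the program. The documents do not support that. If everything elicited at Visit #1 were counted as before, that period would have the full history and focused questions, while the later call lists only a medication history. Outside therapy begun after Visit #1 could then be missed and the count could be biased downward.

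A reader might also take 3.6-fold as the expected distortion. It is not. The 27.9% is a literature lower bound for conversations, not this clinic's charting rate among women already using a treatment, and the figure applies only to outside items.

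Section 5.3 adds that the information is routinely collected as standard of care, and the Visit #1 items carry the same mark (S) in the schedule. That may mean earlier charting was better than Section 2.0 suggests. It does not restore symmetry, since Section 4.3.1 calls the sexual-health focus additional and the repeat medication history exists only after Visit #1. The mark R on that repeat history has no legend in the text shown, and nothing here depends on reading it as research.

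Finally, the objectives, the numerical goals and the planned patient comparison all rest on the FSFI, in a small pilot. That is correct and limits the weight of the point.

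**Conclusion.** The point holds in conditional form. Followed as Section 1.0 words it, the chart count can rise with no change in care, because elicitation is added only from Visit #1 and no start date is collected for treatments. The effect is confined to treatments and referrals not ordered in-house.

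Its size cannot be derived from the documents. Under the assumptions shown, the count of outside items inflates 1.25-fold at 80% earlier capture and 3.6-fold at 27.9%, less in the total count, and not at all if earlier charting was complete.

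It would go too far to conclude that the whole count is an artefact. A referral ordered in-house at Visit #1 is a real order, and this mechanism does not touch it. The FSFI outcome is also unaffected. The point is still worth acting on, because Section 1.0 names the count as a measure of effectiveness and because the missing item is a data field, which an analysis plan cannot supply afterwards.

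**What to change.** Amend Sections 5.3 and 6.3 as follows:

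- Add a field for each sexual-dysfunction treatment and referral, with its start or order date and whether it was ordered in-house.
- Assign items by that date, not by the date first charted. Items in place before Visit #1 count as before, even when first elicited there. Items ordered or started at or after Visit #1 count as after, which gives orders made at Visit #1 itself a defined place.
- Ask the same items at the telephone call, so that the later period is not ascertained less fully than Visit #1.
- Make in-house orders the main comparison, since they are captured alike in both periods, and show patient-reported or outside items separately.

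The cost is a few structured fields in two contacts already scheduled, a slightly longer call, and some reliance on recall for the start dates of outside items. The reported increase may be smaller.

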4.0 Study Population

4.1 Inclusion Criteria

Patient Cohort

- Patients with a gynecologic cancer history
- Patients ages 30-65 years old
- Patients must have completed cancer treatment within the past 12 months
- Patients may be on maintenance therapy

Nurse Cohort

- Registered Nurses 18 years or older
- Registered Nurses working in the gynecologic clinic in the outpatient cancer center

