5.2 Study Design and Duration

Patient Cohort

The study design is an evidence-based practice (EBP) study and includes the implementation and evaluation of a nurse led sexual health clinical program via the FSFI survey. The duration of study participation is 12 weeks. The goal for patients is to have 80% of participating patients to complete pre and post surveys and APP visit as part of their sexual health clinical program, with 30% of patients reporting improvement in sexual dysfunction via the FSFI score.

Nurse Cohort

The study design is an EBP study and includes two surveys in the Registered Nurse participants that includes KAP and EPBSE. The duration of study participation is 4 weeks. The goal is to have 100% of the gynecology oncology registered nurses to participate in the survey and sexual dysfunction education.

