6.2 Time Period of Data under Review

- Data will be collected from/at the following time points: 1-2 times a week from September 2025 to April 2026.
- Information will be kept for no longer than 1 year.

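### The before/after number of referrals and treatments has no common window or person-time denominator, so it is confounded with observation time

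*Protocol*

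**What the plan says.** Section 1.0 of the protocol assesses the effectiveness of the program "via number of referrals and treatments in the chart before and after the intervention in gynecologic cancer patients". Section 5.3 repeats this as a chart-review task, to "count the number of referrals and treatments for sexual dysfunction before and after the nurse led sexual health clinical program intervention". The charts are those of the enrolled patients ("This study involves review of medical records of patients included in this study"), so the same patients supply both sides of the comparison.

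Four other places bear on how much time each side covers:
- Section 4.1: "Patients must have completed cancer treatment within the past 12 months".
- Sections 1.0 and 5.2: "The total patient study participation is 12 weeks", and again "The duration of study participation is 12 weeks".
- Section 5.3 places the second FSFI "after the telephone follow up call performed 8-10 weeks post APP visit".
- Section 6.2 has data collected "1-2 times a week from September 2025 to April 2026".

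Section 6.3 lists referrals to, and visits with, several services without a date limit. It lists dates for surgery, chemotherapy and radiation but none for a referral. The schedule in Section 5.1 makes referrals part of Visit #1. Section 8.3 describes patient-cohort methods for sexual function and does not mention the referral count.

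**The concern.** The measure is a number of events on each side of a visit. It is not a rate, a proportion of patients, or a count over a fixed period. The number of events in a chart grows with the length of chart that is read. If the two sides differ in length, and by a different factor in each patient, the contrast mixes any change in referral practice with the difference in time observed.

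At stake is one of the two patient-level measures of effectiveness in Section 1.0. With referral practice unchanged, the count could fall in patients long past treatment and rise in those who have just finished. The result would then depend partly on the mix of time since treatment among at most 35 patients. Section 8.2 says the project is meant to inform practice change, so a count that cannot be read as a change in practice serves it poorly.

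**Working it through.** The protocol gives no window, rate or target for this count, so there is no figure to reproduce. The check is person-time arithmetic.

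**Inputs**
- Time since treatment: 0 to 52 weeks (Section 4.1, an eligibility limit). I use 4, 26 and 52 weeks as examples.
- Time after Visit #1: 8 to 10 weeks to the last scheduled contact (Sections 5.1 and 5.3), or at most 12 weeks of participation (Sections 1.0 and 5.2).
- Completers: 35 × 0.80 = 28 (Section 8.1).
- Assumption, for illustration: a constant event rate and no program effect.

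**Formula.** Expected count = patients × rate × window length. With the same patients and the same rate on both sides, the expected after/before ratio is the after window divided by the before window.

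| Before (weeks) | After 8 | After 10 | After 12 |
|---|---|---|---|
| 52 | 8/52 = 0.15 | 10/52 = 0.19 | 12/52 = 0.23 |
| 26 | 8/26 = 0.31 | 10/26 = 0.38 | 12/26 = 0.46 |
| 4 | 8/4 = 2.0 | 10/4 = 2.5 | 12/4 = 3.0 |

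Equal windows give 1.00.

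**As counts.** Assume 1 event per patient-year in 28 completers, with 12 weeks after. The expected after count is 28 × 12/52 = 6.5. The expected before count is:
- 28 × 52/52 = 28.0 with 52 weeks before;
- 28 × 26/52 = 14.0 with 26 weeks before;
- 28 × 4/52 = 2.2 with 4 weeks before.

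The same unchanged practice looks like a steep fall in the first two cases and a rise in the third.

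**Calendar reading.** Suppose instead that Section 6.2 is the chart period, taken as 1 September 2025 to 30 April 2026 (241 days, about 34 weeks). A visit on 15 September has about 2 weeks before and 32 after. A visit on 1 February has about 22 before and 13 after. The sides are still unequal, and the imbalance now follows the enrolment date.

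**Referrals at Visit #1.** These come from a single visit and do not scale with weeks of follow-up. If, as an assumption, each of the 28 completers received one at Visit #1 and it were counted as after, the 52-versus-12-week case would become 6.5 + 28 = 34.5 after against 28.0 before. That one classification, which the protocol does not make, would turn an apparent fall into an apparent rise.

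**The case against.** The strongest reply is that windows and denominators are often left to a statistical analysis plan, which is not at hand, and that silence on them is no defect. This stands for silence alone. Here, however, the protocol names the measure in two places as a plain number before and after, in patients whose available time differs widely. The look-back also decides what is abstracted under Sections 5.3 and 6.3, which is a protocol matter.

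A reader might infer that the plan compares 12 months before with 8 to 12 weeks after. It does not say so. The 12 months is an eligibility limit, the 12 weeks is participation time, and the 8 to 10 weeks times the follow-up call and second FSFI. Chart follow-up of early patients could run to April 2026, and the before side can be the shorter one.

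A reader might also take 8/26 to 10/26, an apparent fall of 62% to 69%, as the expected error. The documents do not support that either. It assumes a constant rate and an even spread of time since treatment, whereas referrals at Visit #1 raise the after count by design. A longer before window also works against the program, so the distortion need not flatter it.

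Finally, the count carries limited weight. Sections 3.0, 5.2, 6.1 and 8.1 rest the patient objective, evaluation and goals on the FSFI, and Section 8.3 plans no test of the count. This stands and lowers the severity.

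**Conclusion.** The point holds in a limited form. The protocol names a raw before/after number of referrals and treatments as a measure of effectiveness, with no common window and no person-time denominator. On either natural reading of the available time, the two sides are unequal and differ by patient, so the contrast is confounded with observation time and cannot be read as a program effect.

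The direction and size of the distortion cannot be fixed from the document. In the illustrative table the no-effect after/before ratio runs from 0.15 to 3.0, given a constant rate, 4 to 52 weeks before and 8 to 12 weeks after. An unlimited look-back would widen that range, and Visit #1 referrals add a separate upward shift. Severity is modest: this is a process measure beside the FSFI in a pilot, but the defect is real and cheap to repair.

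**What to change.** In Sections 1.0 and 5.3, replace the raw number by a within-patient comparison over equal windows on each side of Visit #1. An example is any referral or treatment for sexual dysfunction, yes or no, in the 10 weeks before and in the 10 weeks from Visit #1. If the full chart history is to be used, report a rate per patient-month instead.

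Report referrals made at Visit #1 separately from later ones, because they are part of the intervention. Add the date of each referral or treatment to the data elements in Section 6.3. Date elements are already ticked in that section's identifier list.

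The cost is a sentence or two in each section and one more date per event from the same chart review. Fewer before events will be counted. For patients who finished treatment less than 10 weeks before Visit #1, the before window reaches into the treatment period, and these patients should be flagged in the report.

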3.0 Study Purpose and Objectives

Patient Cohort

The primary objectives of this study are to implement and evaluate the effectiveness of a nurse led clinical program to improve sexual dysfunction among gynecological cancer survivors. The patient's outcomes will be measured via the Female Sexual Function Index (FSFI).

The secondary objectives of this study are to improve gynecologic cancer nurses' knowledge and confidence in the topic of sexual dysfunction screening, treatment, and referral using the Knowledge, Attitude, and Practice Survey in Healthcare (KAP), and the Evidence Based Nursing Practice Self-Efficacy Scale (EPSE).

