 - o Access to "About Us" sexual dysfunction patient and provider handouts
 - o National Comprehensive Cancer Network Sexual Health Guidelines

Questionnaires/Surveys:

Patient Cohort:

We will be doing the following questionnaires for patient participants:

- Female Sexual Function Index (FSFI)
 - o The FSFI is a validated tool that addresses five domains: desire, subjective arousal, lubrication, orgasm, satisfaction, and pain/discomfort. It encompasses nineteen self-measurement items that provides a score on overall levels of sexual function (Meston et al., 2020).

Nurse Cohort:

We will be doing the following questionnaires for nurse participants:

- Knowledge, Attitude, and Practice Survey in Healthcare (KAP), and the Evidence Based Nursing Practice Self-Efficacy Scale (EPSE).
 - o The questionnaire is not available in languages other than English.
 - The KAP survey is a validated tool that assess knowledge and attitudes about a specific health topic, to identify areas where education efforts need to be applied (Andrade et al., 2020).
 - The EBPSE survey is a validated tool which assesses and monitors nurses' confidence in their ability to implement evidence-based practice (EBP) skills (Tucker et al., 2009).

The study will be conducted at one site only, Cedars-Sinai.

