- In the next survey, EBPSE, we will assess nurses' responses in aggregate form. The EBPSE survey is comprised of 17 items designed to help nurse process information and develop essential EBP skills. Each item is rated on how confident one can perform the activity with percentage numbers 0-100 likert scale (Tucker et al., 2009).
- We hypothesize that 50% of nurses have an increase in EBPSE scores indicated by a ½ standard deviation.
- The project will utilize both QI Macros and Intellectus Statistics to measure the changes in nurses' knowledge and self-efficacy. The analysis will incorporate statistical methods such as run charts, control charts, and t-tests to evaluate changes in participants' knowledge and self-efficacy. More specifically regarding t-tests, the EBPSE will use a paired sample t-test, and the KAP survey will use t-tests to compare pre and post survey responses.

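### The only nurse scale described as measuring confidence (EBPSE) covers general evidence-based-practice skills, so its hypothesis gives no direct evidence on confidence in sexual dysfunction care

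*Protocol*

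**What the plan says.** **Objective.** The nurse-cohort purpose in Protocol Section 1.0 is to "increase knowledge and confidence in sexual dysfunction screening, referral and treatment among gynecologic cancer nurses". Section 3.0 repeats it as the secondary objective: to "improve gynecologic cancer nurses' knowledge and confidence in the topic of sexual dysfunction screening, treatment, and referral". Both sections name the KAP and the EBPSE (also abbreviated EPSE and EPBSE, and treated here as one scale) as the instruments. Section 5.3 likewise plans to "assess the nurses' knowledge and confidence using the KAP and EPSE survey" before and after the education.

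**EBPSE.** Section 5.3 says that it "assesses and monitors nurses' confidence in their ability to implement evidence-based practice (EBP) skills". Section 8.3 describes it as "17 items designed to help nurse process information and develop essential EBP skills" and adds: "Each item is rated on how confident one can perform the activity", on a 0-100 scale.

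**KAP.** Section 5.3 says that it is used to "assess knowledge and attitudes about a specific health topic". Section 8.3 gives 24 items, rated 1 to 4 for adequacy of knowledge and skills and for frequency of practice, with knowledge, attitude and practice subscales.

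**Education.** The programme in Section 5.3 "aims to normalize sexual health discussions, build provider confidence, and guide appropriate referrals". It consists of a short-message workshop, patient and provider handouts, and national sexual health guidelines.

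**Hypothesis.** Section 8.3 expects 50% of nurses to gain ½ SD on the EBPSE, and separately 50% to gain ½ SD on the KAP. It describes the nurse analysis as one of knowledge and self-efficacy.

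**The concern.** The confidence that the protocol wants to change concerns a clinical topic: screening for sexual dysfunction, referring and treating. The confidence that the EBPSE records, as described, concerns the general skills of evidence-based practice. A nurse can gain one without the other.

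Two misreadings follow if the plan is carried out as written:

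- A gain on the EBPSE could be reported as greater confidence in sexual dysfunction care, which it would not show.
- A flat EBPSE could be taken to mean that the education failed to build that confidence, although the scale, as described, did not ask about it.

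Section 8.2 says that the project is meant to inform practice change, so the wrong inference could carry into a decision about the education programme. A later analysis plan cannot repair this, because it cannot supply ratings that the survey never collected.

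**Working it through.** No power or sample-size figure enters this point, and the protocol gives none for nurses. The check is a comparison of what is to be learned, what is asked and what is taught.

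1. **Construct in the objective (Sections 1.0 and 3.0).** Knowledge and confidence, both tied to screening, referral and treatment of sexual dysfunction.

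2. **Which instrument measures confidence (Sections 5.3 and 8.3).**
   - KAP: tied to a health topic. Its subscales are knowledge, attitudes and practices. None is called confidence or self-efficacy.
   - EBPSE: described as confidence, item by item. It is the only nurse instrument so described, and so the only source for the self-efficacy part of the nurse analysis in Section 8.3.

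3. **Confidence in what (Sections 5.3 and 8.3).** Both descriptions of the EBPSE give the same object, EBP skills. Neither mentions sexual health, and no section says that the items were reworded or supplemented for this project. The items themselves are not listed.

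4. **What the nurses are taught (Section 5.3).** Sexual-health communication, handouts and guidelines. No training in EBP skills as such is described. The guideline material is evidence-based, so the education has some link to EBP, but the link is indirect.

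5. **Closest topic-specific data (Section 8.3).** On the KAP, nurses rate their own knowledge and skills from 1 (inadequate) to 4 (more than adequate). Rating one's skills as adequate is near to confidence but is not the same thing, and the protocol does not name these ratings as the confidence measure.

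6. **What the criterion would rest on.** With the maximum of five nurses, 50% is 0.5 × 5 = 2.5. If the hypothesis means at least 50%, three of five nurses must gain ½ SD on the EBPSE. Whether that count is met says something about general EBP self-efficacy. It says nothing direct about confidence in sexual dysfunction care, whatever the number of nurses.

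Set side by side, the objective is topic-specific, the confidence scale is general as described, and the topic-specific instrument has no confidence subscale.

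**The case against.** **The KAP also serves the objective.** This stands in part. Sections 1.0, 3.0 and 5.3 assign the KAP and the EBPSE together to knowledge and confidence. Reading the KAP as the knowledge measure and the EBPSE as the confidence measure is an inference, though the wording of the analysis in Section 8.3 makes it a natural one. A reader might conclude that the confidence objective cannot be answered at all. The documents do not support that, because the KAP knowledge-and-skills ratings give a partial, topic-related answer.

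**The 17 items are not shown.** This also stands. A reader might infer that not one of them touches sexual dysfunction. The protocol gives only a summary and does not list the activities being rated. What can be said is that no sexual-health content or adaptation is described.

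**An EBP scale suits an EBP project.** Sections 5.2 and 8.2 do call this an evidence-based-practice project, and the education includes guidelines. It would therefore be too strong to say that the scale has nothing to do with the intervention. But that label describes the type of project; the objectives name sexual dysfunction care.

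**The stakes are small.** True as to scale: a secondary objective, at most five nurses, and no claim to generalizable knowledge. Small numbers limit precision. They do not turn a measure of one construct into a measure of another.

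**Validated scale against ad hoc items.** Section 5.3 calls the EBPSE validated, and added items would not be. This is a fair cost, but validation for EBP skills does not carry over to confidence in a clinical topic.

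**Conclusion.** The point holds in a limited form. The nurse objective includes confidence in sexual dysfunction screening, referral and treatment, while the only instrument described as measuring confidence is described as covering general EBP skills. The EBPSE hypothesis gives no direct evidence on topic-specific confidence, and the KAP self-ratings supply only a partial proxy.

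The effect is confined to the confidence part of the secondary objective. It does not touch the KAP knowledge result or the patient outcomes. The change should be made, because it is cheap and cannot be made after the baseline survey.

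The conclusion assumes that the protocol's description of the EBPSE is accurate and that the scale is used unadapted. If the items have been adapted to sexual health, saying so in Sections 5.3 and 8.3 would resolve the point.

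**What to change.** **Preferred.** Before any nurse completes the pre-survey:

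- Add brief confidence items on screening for, referral for and treatment of sexual dysfunction (one each would do) to the same pre and post survey, rated 0-100 as the EBPSE already is.
- In Sections 1.0, 3.0 and 8.3, tie the confidence objective to these items.
- In Section 8.3, restate the EBPSE hypothesis as one about general EBP self-efficacy.

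**If no items can be added.** Tie the confidence claim to the KAP knowledge-and-skills ratings, call them a proxy, and state that EBPSE results will not be interpreted as confidence in sexual dysfunction care. This is also the only route left if baseline surveys have already been completed, since a missed baseline cannot be recovered.

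**Cost.** A short amendment to the protocol and survey, and a slightly longer questionnaire. The added items are not a validated scale, and the report should say so. The fallback needs wording changes only, but leaves confidence measured indirectly.
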